**A Trial of Behavioral Economic Interventions Among Food Pantry
Clients**

NCT04011384

2022-09-27

IRB Study Protocol and Analysis Plan

Protocol

Objectives

Overall objectives

The objectives of the study are to evaluate the influence of a web-based behavioral economic intervention compared to a control group on the following outcomes among food pantry clients:

- Nutritional quality of food chosen at the pantry using food transaction data
- Fruit and vegetable intake measured by dermal carotenoids (a fruit and vegetable biomarker) and a food frequency questionnaire
- Objectively measured height, weight, and blood pressure

Background

Poor dietary habits and food insecurity are significant public health problems: Unhealthy dietary habits are associated with obesity, cardiovascular disease, type 2 diabetes, and certain cancers (1). To comprehensively address these chronic diseases, interventions need to focus on calorie reduction and changing specific dietary habits. For example, potato chips and sweetened beverages are two foods with the strongest links to long-term weight gain, suggesting a need to focus on decreasing their consumption, while vegetables, fruits, whole grains, nuts, and yogurt are protective against weight gain (22). Low-income individuals are at particularly high risk for poor dietary quality and obesity (2-4). Further, it is estimated that 14% of U.S. households experience food insecurity, or insufficient access to safe and nutritious foods (5), which occurs more commonly among low-income, racial/ethnic minority, and immigrant families in the U.S (5). Food insecurity has been associated with low nutrient intake and poor diet (6-9), and a host of negative health outcomes, including hyperlipidemia, hypertension, diabetes (10, 11), depression and anxiety (12, 13), obesity in women (14, 15), and poor maternal mental health (16). The proposed research is focused on clients of a food pantry in Philadelphia, PA that serves a low-income population. Food insecurity among this group is largely concentrated in four sub-sets of the community we will be studying: a) seniors; b) Russian immigrants; c) Orthodox Jewish families with four or more children; and d) those with mental illness. The majority (60%) of these low-income individuals are enrolled in the supplemental nutrition assistance program (SNAP). The food pantry provides their clients with five to seven days worth of meals each month and internal surveys conducted by the pantry reveal that clients report consuming the vast majority of food provided.

Psychological and behavioral economic insights to inform health interventions: There is growing interest in using behavioral science techniques to nudge consumers to make healthier choices, while preserving freedom of choice. One fundamental psychological insight is that two systems of thought operate simultaneously in the human brain, commonly referred to as System 1 and System 2 (23). System 1 thinking is faster (impulsive, reflexive, emotional, and impatient) whereas System 2 thinking is slower (deliberative, controlled, analytical, and patient). System 1 produces an automatic response whereas System 2 produces a reasoned response. The function of System 2 is to monitor the activities of System 1, which requires attention and effort. However, when one's cognitive resources are stretched (for example, when thirsty, hungry, stressed, or in a distracted state), System 1 dominates. Part of the reason humans rely so heavily on System 1 is because we have a limited ability to attend to, process, and remember information (23). This often leads to difficulty remembering and acting upon information that is overly complex. A number of studies have demonstrated that strategies that boost salience and convenience of healthy food options encourage greater selection of those foods in the short-term. Such strategies include serving healthier options at the beginning of a buffet line (24), placing less healthy food in opaque containers so it is out of sight (25), and making water highly visible and accessible (17). In the proposed research, we leverage the following four insights from psychology and behavioral economics:

Status quo bias and default options: Even when beliefs and preferences align with healthy choices, people often choose unhealthy options simply because the choice context promotes them. Status quo bias is the strong tendency to stick with whatever options happen to be the current default (26). For example, countries that automatically enroll people as organ donors have dramatically higher donor rates versus countries where people must opt-in to be a donor (19) and default settings can dramatically increase generic medication prescriptions (20). In the proposed research, we will leverage the status quo bias by pre-populating the shopping baskets of food pantry clients with several healthy, preferred items targeted towards a clients health needs as the default (clients can opt to remove them).

Healthy placement choice architecture: Choice architecture refers to the context in which people make decisions, including what choices are offered and how they are displayed and communicated. Our research has shown that a simple choice architecture nudge displaying bottles of water so they are more visible and accessible in a cafeteria

setting increased purchases of bottled water (17, 18). In the proposed research, we will implement a choice architecture intervention that will place the healthiest options at the top of the webpage for each food category so they are more visible and prominent.

Simple and salient information: Part of the reason humans rely so heavily on System 1 is because we have a limited ability to attend to, process, and remember information (23). This often leads to difficulty remembering and acting upon information that is overly complex, like our current nutrition labels that present lots of numbers, percentages, and serving sizes requiring math calculations on the fly. The traffic light nutrition messages we are testing in this study are designed to engage System 1 by making messages salient and easy to understand. Traffic light labels draw upon automatic associations people have between red and stop and green and go to facilitate immediate cognitive processing. Our team has demonstrated that a traffic light labeling intervention in a hospital cafeteria was associated with a 4-percentage-point decline in sales of unhealthy items and a 5-percentage-point increase in sales of healthy items in a hospital cafeteria over two years (17, 18). We will also use salient messaging to draw attention to discounts for healthier foods (e.g., save 1.5 points by switching from white to brown rice).

Social norms messaging: Human behavior is often influenced by social norms, and most health behaviors are performed within a social context (27). For instance, most people tend to eat meals in the presence of others and are unconsciously influenced by the eating behaviors of their companions. A person is more likely to eat more when he observes that his companion (especially a thin person) is overeating at a meal.(28) Conversely, when others at the table order just the soup and salad for lunch, an individual might be less likely to order the cheeseburger and fries on the menu.(28) Social norms messaging has also been found to influence people in other domains such as increasing environment-friendly behaviors (21). For these reasons, our fourth intervention will display social norms messaging indicating the healthy products most commonly selected by pantry clients (e.g., over half of all customers order bananas when shopping here).

Very few food pantry interventions have been tested: Food pantries are an important way to address food insecurity in the U.S., with 1 in 7 adults accessing food through pantries and meal service programs (5). Historically, food pantries have focused on providing access to free food for those in need, without considering the nutritional quality of food provided. That is now changing. Food pantries are increasingly offering healthier items, but few studies have rigorously tested ways to promote healthier food selections among low-income clients at food pantries. Very few randomized-controlled trials (RCTs) of nutritional interventions have been conducted in food pantries. One such study enrolled individuals with diabetes in a six-month RCT that provided diabetes-appropriate foods, blood sugar monitoring, primary care referral, and self-management support (29). The intervention led to improvements in glycemic control, fruit and vegetable intake, self-efficacy and medication adherence (29). Another RCT found that a motivational interviewing intervention combined with referrals to community services led to a one serving per day increase in fruit and vegetable intake and decreases in food insecurity (30). However, both of these interventions are costly as they require trained personnel to carry out the interventions. One food pantry study tested low-cost, behavioral nudges designed to increase the salience and convenience of healthy foods. In that study, researchers found that moving the placement of protein bars from the end to the front of a dessert line increased selection of those items over less healthy desserts (odds ratio: 1.69) as did placing the bars in sealed, clear plastic bags instead of their original packaging (odds ratio 1.92) (31). This study provides some of the first evidence that such strategies can encourage healthier choices in a food pantry context serving very low-income individuals, but this was a short-term intervention with data on only one food choice outcome. Our proposed research will make a significant contribution beyond existing research by evaluating the influence of a suite of evidence-based behavioral nudges among food pantry clients over a longer period of time (one-year) and examining more comprehensive outcomes, including the nutritional quality of food selections, dietary intake, and health outcomes.

Significant contributions of the proposed research: The proposed study will be one of the first large, longer-term RCTs testing low-cost behavioral nudges among a very low-income group of consumers. This study will improve upon prior work in several ways. First, we will use a randomized-controlled design to follow a large cohort of clients over one year. Second, we will analyze objective transaction data of all food selections made at the pantry over four months (one month pre-baseline and three months post-baseline) at the individual-level and link that with food intake and health data. Third, we will measure fruit and vegetable intake with an objective biomarker and questionnaire, and we will objectively assess health outcomes including weight and blood pressure. This will also be the first study to evaluate these behavioral techniques in the context of an innovative online ordering platform that has the potential to be the future gold standard for food pantries. Although web-based ordering systems are not yet widespread in food pantry settings, their use is growing rapidly. Two of the largest food pantries in New York City (NY Common Pantry and St. John's Bread and Life) have both implemented an online ordering system and the St

Johns system has been replicated in Nevada. Our food pantry partner has also replicated their online system in a neighboring county and the pantry has hosted site visits and shared best practices with the Metropolitan Council on Jewish Poverty who has 30 distribution sites and is moving toward an online system. This work also makes a significant contribution because very few studies of behavioral nudges have been conducted among populations with very high concentrations of poverty. Finally, our research team represents an interdisciplinary collaboration that includes academic and community partners. This partnership enables us to gain valuable insights from practitioners and ensures the research questions we are asking are relevant to practice as well as scientific discovery. This partnership will also help us disseminate these results through conventional academic channels as well as to practitioners. Given widespread interest in implementing these types of low-cost nudges to improve food choices, such rigorous evaluations are sorely needed.

1. Mozaffarian D. Dietary and policy priorities for cardiovascular disease, diabetes, and obesity: a comprehensive review. *Circulation*. 2016;133(2):187-225.

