

Study Design

Design

We will use a random number generator to assign study participants to one of 2 conditions: 1) usual care (control); or 2) behavioral economic intervention. The research team will create the randomization list and a research assistant will assign the participant to the correct online platform condition, but the investigators and data analysts will remain blind to group assignment. This study will contain two parallel groups. Although participants will not initially be aware of the other study condition, they will not be blinded to study condition because those in the intervention condition will be viewing the altered ordering platform as they shop.

Study duration

This study is estimated to take four years. Year 1 will be spent finalizing the research protocol, updating the food pantry web-platform, categorizing pantry food with traffic lights, and hiring and training study staff. We will begin recruiting participants and collecting data in the second half of year 1. Subjects' participation will be for four months (one month pre-baseline, three months post-baseline). Participant recruitment will continue through years 2 and 3 of the study and data collection will continue through years 2, 3 and the first half of year 4. Year 4 will be spent cleaning and analyzing data and preparing manuscripts.

Characteristics of the Study Population

Target population

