In response to the COVID-19 pandemic, on March 11, 2020, the Mitzvah Food Program at the KleinLife Community Center (where our research study takes place) changed their food order and pick up protocol. No clients are allowed to enter the facility and instead must either order online remotely (maintaining choice selection) or choose a pre-packaged bag that is picked up outside at the door. Study procedures before the start of the COVID-19 pandemic involved participants placing food orders in-person at the food pantry and study staff conducting physical measurements and surveys with participants in-person at the food pantry. These study procedures are detailed below under "Pre-COVID-19 Procedures." Since the start of the pandemic, we have adapted our study procedures to ensure safety for participants and study staff. These new study procedures are as follows.

Participants will be recruited on-site at the Jewish Federation of Greater Philadelphia Food Pantry or remotely by study staff working closely with food pantry staff, following all current COVID-19 safety guidelines. We anticipate that the eventual availability of a vaccine will allow recruitment either remotely or on-site. We will ask participants several screening questions to determine their eligibility. Eligible participants will meet the following criteria:

- 1) At least 18 years old;
- 2) Regularly shops at the food pantry (at least once per month)
- 3) Primary food shopper for household (Only one member of household can participate)
- 4) Willing and able to place orders themselves or with assistance (while still viewing the screen) using the online ordering system
- 5) Willing and able to use a blood pressure cuff and scale provided to them for taking blood pressure and weight.
- 6) We have added the fourth screening criterion to ensure that participants will place online orders even if the pantry is operating remotely. After determining eligibility, we will administer informed consent electronically using the REDCap electronic-consent (e-consent) framework, detailed in the informed consent section of this protocol. We will offer to read the consent form and talk through the process with participants, and we will provide the option of paper consent forms for any participants not comfortable with the electronic consent process.

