Following baseline measurements, participants will be randomized to one of two conditions: 1) the usual care group (control); or 2) the behavioral economic intervention.

To encourage participants to place orders using the food pantry's SmartChoice online ordering system, we will incentivize shopping by paying participants for successfully placing each order. We will train research participants on how to use the SmartChoice system via a walkthrough with study staff prior to their first order, for which they will be remunerated \$25. Participants will be remunerated for each order as follows: \$5 for baseline, \$3 for the first two months of participation, and \$4 for the third month of participation. We will provide printed online order guides to support online ordering (fp_Online Order Guide). We will also offer four months of contactless food delivery. Contactless means that when the Research Assistant brings the food to the study participant's home, they will place the food at the door, knock or ring the doorbell, and wait at a safe distance as the participant picks up the food. We will use phone and text messaging through Mosio, a secure text messaging platform, to communicate with participants using text message templates (fp_Text_Message_Templates).

Deliveries will only be offered to those participating in the study remotely, and for that reason we have removed any information about deliveries in our informed consent forms.

Three months after baseline, we will conduct 3-month measurements of weight, blood pressure, and diet quality using the Veggie Meter with participants at their homes or at the food pantry following all current COVID-19 safety guidelines. We will administer the diet survey again electronically through a REDCap survey. We will not administer the health survey at 3-months. We will provide the option of doing the survey over the phone on an as-needed basis for participants not comfortable with electronic surveys. Participants will receive \$25 for completing all components of 3-month measurements (\$10 for the survey, \$5 for blood pressure, \$5 for weight, and \$5 for veggie meter). We will provide participants with their blood pressure and weight results at the time of measurement using printed cards.

Food delivery will end after four months. We will use a post flyer to inform participants of their last food delivery (fp_PostCards Last Delivery).

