Participants will be allowed to visit the pantry at their normally scheduled time to allow for convenience for the participant. During each visit, participants will order their grocery items using the web-based touchscreen system. The web-based ordering platform at the food pantry, will enable us to easily capture and evaluate all food selections at the pantry over one year per participant. Once orders are placed, a receipt is printed out and food pantry staff fill the order. Before participants place their order, study staff will measure participant weight, height, and blood pressure in a private room, which is estimated to take approximately 5 minutes. To ensure standardized weights over time, trained research assistants will follow a clear protocol (participants will be instructed to wear light clothing, no shoes for weighing, and each participant will be weighed twice on a digital scale). Height will also be assessed to the nearest 1/8 inch using a stadiometer. Participants will then be given the Block Food Frequency Screener in order to measure their fruit and vegetable intake. The screener includes questions about usual fruit and vegetable intake and takes about 5 minutes to complete. Participants were then given a health questionnaire. Participants will have their dermal carotenoid levels measured with a Veggie Meter, a non-invasive device which uses reflection spectroscopy to measure the pigment in the skin which corresponds to fruit and vegetable intake.

Originally, after attending the food distribution at each time point, participants were instructed to visit a nearby LabCorp to complete a blood draw that measured a fruit and vegetable biomarker (beta carotene serum levels) and HbA1c. Blood measurements will also include a lipid panel (total cholesterol, LDL, HDL, triglycerides, and glucose), c-reactive protein, and serum glucose. However, this proved unreliable and burdensome, so the lab tests were eliminated and replaced by the aforementioned dermal carotenoid measurement in October 2019. This did not change the incentive structure. Those who were previously offered LabCorp appointments were given the opportunity to continue going if they so chose, but were not required to have blood work done for study participation.

The following documents are currently attached to this item:

There are no documents attached for this item.

Deception

Does your project use deception?

No

International Research

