Are you conducting research outside of the United States?

No

Analysis Plan

Data will be descriptively summarized and evaluated for quality prior to the evaluation of primary and secondary endpoints. Means and standard deviations will be used to characterize continuous variables such as weight and blood pressure, and frequencies and percentages will be used to describe categorical variables such as nutritional quality. Medians and interquartile ranges will be reported for continuous variables that exhibit skewness. Data will be descriptively summarized overall and by condition. All outcomes will be analyzed at the customer level except for nutritional quality, which will be analyzed at the item level. Analyses will employ population-averaged marginal models estimated by Generalized Estimating Equations (GEE) to account for correlations among longitudinal monthly measurements and items purchased per food pantry customer. Marginal models estimated by GEE are advantageous for their population-level interpretation and robustness of estimated effects to the assumed correlation structure among repeated measurements (meaning unbiased estimates of the effect of the behavioral economic intervention will be obtained whether or not the correlation among repeated measurements within a food pantry customer is modeled correctly). Clusters will be defined at the level of the customer for all analyses, and independence working correlation will be assumed. Linear models will be used for continuous outcomes and logistic models for ordinal outcomes such as nutritional quality. Models will include 2-level intervention, month, and the interaction of intervention and month as categorical variables. The primary analysis of testing the effectiveness of the behavioral economic arm compared to the control arm will be evaluated by the joint test of the null hypothesis test that intervention-month interaction coefficients are 0, denoting no difference in the change in respective outcomes from baseline to month 3 between intervention groups. Secondary analyses will test for changes in intervention effects over time by testing whether intervention-month interaction coefficients are equivalent at month 3. We will evaluate the sensitivity of estimated intervention effects to imbalances in baseline covariates and missing data. To assess the impact of imbalance in baseline covariates, outcomes will be reanalyzed in models that adjust for baseline covariates that differ significantly at the 0.05 level by intervention arm. We will evaluate sensitivity to missing data by inverse probability of weighted GEE and multiple imputation. The Holm procedure⁷⁷ at a family-wise error rate of 0.05 will be used to account for multiple comparisons in testing differences in five primary outcomes between the two groups (nutritional quality of food selected, fruit and vegetable intake based on the food frequency questionnaire, weight, and blood pressure). Similar analyses of dermal carotenoids will be performed as secondary endpoint analyses.

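### The primary food-order test measures change from a single order month; using that month as a covariate would recover precision without new data

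*Combined protocol and SAP*

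**What the plan says.** **Reference period.** The Background (significant contributions) describes "transaction data of all food selections made at the pantry over four months (one month pre-baseline and three months post-baseline", and Study duration agrees: "Subjects' participation will be for four months (one month pre-baseline, three months post-baseline". Under Procedures four orders are paid for: baseline and months 1, 2 and 3. The order outcome thus has one reference month and three follow-up months.

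**Analysis.** The Analysis Plan states: "Models will include 2-level intervention, month, and the interaction of intervention and month as categorical variables". Clusters are customers, the working correlation is independence, and the primary test is that all interaction coefficients are zero. Nutritional quality is a primary outcome under the Holm procedure and is analysed per item by a logistic model. Covariate adjustment appears only as a sensitivity analysis, for baseline covariates that differ between arms at the 0.05 level.

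**Earlier orders.** The second eligibility criterion is "Regularly shops at the food pantry (at least once per month". Under Pre-COVID-19 Procedures, "During each visit, participants will order their grocery items using the web-based touchscreen system", and the platform "will enable us to easily capture and evaluate all food selections at the pantry over one year per participant". Since March 2020, however, clients "must either order online remotely (maintaining choice selection) or choose a pre-packaged bag that is picked up outside at the door". No section says that item-level orders from before enrolment are kept or can be released to the study.

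**The concern.** One month's basket is a noisy measure of what a client usually chooses. With arm, month and their interaction all categorical, every interaction coefficient subtracts that same month, so its noise enters all three coefficients of the joint test. Nothing in the primary model offsets this. Conditioning on the reference month, rather than subtracting it in full, would remove part of the noise using data the trial already collects. At stake is power for a primary outcome that must also pass a Holm adjustment over five outcomes (first step 0.05/5 = 0.01).

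**Working it through.** **Inputs.** From the documents: one reference month, three follow-up months, independence GEE, joint interaction test, target 500. Not given: the SD, the month-to-month correlation, an effect size or a power figure. I set the SD of a client's monthly healthy share to 1 and vary ρ over 0.3, 0.5 and 0.7. I take the reference order to be placed before the altered platform is shown. The scale is linear and per client, so the results illustrate the item-level logistic model and do not reproduce it.

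**The plan's own figure.** 61 complete + 439 to recruit = 500, which agrees. No calculation supports the 500, so its power cannot be reproduced.

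**1. Planned contrast.** The month-3 interaction is the arm difference in Y3 − Y0, with per-client variance 2(1 − ρ) = 1.40, 1.00, 0.60.

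**2. Reference month as covariate.** The residual variance is 1 − ρ² = 0.91, 0.75, 0.51. The ratio to step 1 is (1 + ρ)/2 = **0.65, 0.75, 0.85**.

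**3. Joint test.** Let I be the identity and J the all-ones matrix over months 1 to 3. The covariance is (1 − ρ)(I + J) for change and (1 − ρ)(I + ρJ) with the covariate. For an effect constant over the three months, noncentrality is proportional to 3/[4(1 − ρ)] and 3/[(1 − ρ)(1 + 3ρ)]. The gain is 4/(1 + 3ρ) = 2.11, 1.60, 1.29.

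**4. Adding two earlier months (three in all), equal correlation.** The residual variance is 1 − 3ρ²/(1 + 2ρ) = 0.831, 0.625, 0.388. Against step 2 the further reduction is 1 − 0.831/0.91 = 9%, 1 − 0.625/0.75 = 17%, and 1 − 0.388/0.51 = 24%.

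**5. Decaying correlation.** Under pure AR(1) the latest month carries all the information. The one-month covariate gives a ratio of (1 + ρ³)/2 = 0.51, 0.56, 0.67, and earlier months add 0%. Now let correlation at lag h be s + (1 − s)0.7^h.
- s = 0.3: the lag-3 correlation is 0.3 + 0.7 × 0.343 = 0.540, so the one-month residual is 1 − 0.540² = 0.708. The mean of the two earlier months has variance 0.895, covariance 0.7165 with the reference month and 0.443 with month 3. R² is (0.540² × 0.895 − 2 × 0.540 × 0.443 × 0.7165 + 0.443²)/(0.895 − 0.7165²) = 0.300, so the residual is 0.700, a reduction of about 1%.
- s = 0.4: the same steps take 0.633 to 0.621, about 2%.

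**6. Pooling all earlier orders into one baseline level.** Under independence GEE a client with k orders has weight w = k/k̄ in the baseline mean (k̄ is the average number of orders) but weight 1 at follow-up. The per-client variance is 1 + w²[ρ + (1 − ρ)/k] − 2wρ. Let half the clients have six orders and half one, with ρ = 0.7. Then k̄ = 3.5 and w = 1.714 or 0.286, giving 0.804 and 0.682, mean 0.743. Divided by 0.60 this is **1.24**, worse than the plan. If only 61/500 = 0.122 have six orders, the ratio is **2.02**. At ρ = 0.5 the two ratios are 0.90 and 1.33.

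**The case against.** The arms are randomised, so a change contrast is valid, and without a power calculation nobody can say the trial is short of power. Marginal GEE was chosen for its population-averaged reading, and in a logistic model a baseline covariate turns the arm coefficient into a conditional odds ratio. The correlations used here are assumptions. All of this stands, except that the population-averaged reading can be kept by standardising the fitted results over the whole sample.

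A reader might infer something stronger: that monthly shoppers on a web platform all have order history ready to extract, so that a longer look-back would cut the variance of the month-3 change by 33% with three months or 42% with six, from (1 + 1/k)/2 = 0.667 and 0.583. The documents do not support that reading.
- The sentence about a year of captured selections sits in the pre-COVID procedures and describes follow-up during the study.
- Eligibility requires monthly shopping and willingness to order online; it does not require past online orders. Participants receive a platform walkthrough before their first order.
- 439 of the 500 were still to be recruited at the end of 2020, when a pre-packaged bag was an alternative to choosing items.
- The Background says default items are preferred ones, but not how preference is established.

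The 33% and 42% need complete, equal histories and equal correlation. If only 61 of 500 had three usable months, the average ratio would be 1 − 0.122 + 0.122 × 0.667 = 0.96. Much of the 33% is also available from the one month already collected.

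**Conclusion.** The point holds as one of lost efficiency, confined to the order outcome; it is not bias. The secure part needs no new data: conditioning on the reference month gives 0.65 to 0.85 of the planned month-3 variance for ρ of 0.3 to 0.7 under equal correlation, and 0.51 to 0.67 under pure AR(1) with the same lag-1 values. The gain shrinks as ρ approaches 1. A longer look-back is a conditional extra: a further 9 to 24% with three complete months and equal correlation, about 0 to 2% under pure AR(1) or a strong AR(1) component, and less where histories are incomplete. All figures rest on the linear client-share scale and on assumed correlations. The documents do not support a claim that the trial is underpowered, or that several earlier orders can be had for every client.

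**What to change.** **Analysis Plan, nutritional quality.** Use months 1 to 3 as the response. Enter the client's reference-month healthy share, defined in advance from the traffic-light categories, as a covariate, with a coefficient that may differ by month. Make the primary test the joint test of the arm effects at months 1, 2 and 3. Keep clustering by customer, and report arm effects as standardised marginal differences.

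**Earlier orders.** State whether item-level platform orders from before enrolment can be retrieved. If they can, extract them over a fixed look-back by the same rule in both arms and add the mean of the orders before the reference month as a second covariate. Give clients without earlier orders, including those who took pre-packaged bags, a missing-history indicator and a fixed fill-in value. Do not pool earlier orders into one baseline level under independence GEE.

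**Cost.** The first change needs only Analysis Plan wording. The second needs one larger data extract, an IRB and consent line covering earlier orders, and matching wording in the Background, Study duration and Analysis Plan. Neither adds visits or participants.
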